## 5.1.2 Increase or Reduction in Dose of Study Drug

### 5.1.2.1 Dose Adjustment Rules

All doses, dose decisions and reasons will be documented in the eCRF for both roxadustat and ESAs.

#### Subjects receiving roxadustat

Dose adjustments are permitted on a 4-weekly interval from week 4 onwards and will be aimed at keeping subjects' Hb levels between 10.0 to 12.0 g/dL and will be based upon current Hb levels and change in Hb over the preceding 4 weeks as illustrated in [Table 4](#) (deviation from the 4-week period is allowed anytime during the study in case of excessive hematopoiesis or Hb  $\geq$ 13.0 g/dL).

**Table 4 Dose Adjustment Rules for Roxadustat**

Change in Hb Over Past 4 Weeks (g/dL) a	Hb (g/dL)		
	<10.5	10.5 to <12.0	12.0 to <13.0
< -1.0	↑	↑	No change
-1.0 to 1.0	↑	No change	↓
> 1.0	No change	↓	↓

Hb: hemoglobin

a Subtract first Hb value from last value Hb to calculate the change

- All dose adjustments are made based on Hb values using HemoCue®, a point-of-care device.
- Dose increases by 1 dose step (↑) and reductions by 1 dose step (↓) are pre-set

- If the dose adjustment is ‘No change’ per the above table, the dose remains unchanged and the next dose adjustment review is 4 weeks after that visit.
- The dose steps for roxadustat are as follows: 20, 40, 50, 70, 100, 150, 200, 250, 300, and 400 mg.
- The maximum dose is the dose step corresponding to 3.0 mg/kg (based on postdialysis weight in HD subjects and in PD subjects weight minus abdominal fluid based on last filling) per administration or 400 mg, whichever is lower. At study visits where weight is collected the default weight and maximum allowed dose step for a subject will be adjusted if the weight change is  $\geq 5\%$  compared to the previous default weight collected in the study. Initial default weight is weight at randomization visit.
- If there is a safety concern, investigators may deviate from the dose adjustment rules for roxadustat. This should be discussed with the medical monitor and documented in the source documentation.
- Contact the medical monitor if dose adjustments would lead to doses outside the limits of the dose step range; i.e. lower than 20 mg or higher than 400 mg.

In the following cases dose adjustment may be made at any time outside the 4-weekly interval:

- Dose reduction in case of excessive hematopoiesis
- Dose increase by 1 step in case subject Hb  $< 9.0$  g/dL (HemoCue®) and no dose adjustment occurred in the preceding 4 weeks.

At any time when Hb  $\geq 13.0$  g/dL

- Stop dosing
- Resume dosing when Hb  $< 12.0$  g/dL at a dose that is reduced by 2 steps
- Next dose adjustment review is 4 weeks after dose resumption and in 4-weekly intervals thereafter.

Dose Adjustment for Excessive Hematopoiesis

At any time during the Treatment Period:

- If Hb increases by  $>2.0$  g/dL at any time within 4 weeks, the dose should be reduced by 1 dose step

Note: Only 1 dose reduction for excessive hematopoiesis is recommended within a period of 4 weeks. If a blood transfusion has been performed or a course of ESA rescue therapy has been administered within 2 weeks of meeting the criteria for excessive hematopoiesis, it is recommended not to perform a dose reduction for excessive hematopoiesis.

After a dose adjustment due to excessive hematopoiesis, the subject’s next dose adjustment review will occur 4 weeks later, and in 4-weekly intervals thereafter.

If the dose adjustment interval falls on a non-visit study week, the dose adjustment review should be performed at the next scheduled study visit.

All dose decisions should be documented in the subject source data.

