Subjects should take roxadustat in a consistent manner relative to their phosphate binder intake, and discuss with the investigator before changing their phosphate binder dose or dosing time. As a further risk mitigation this study protocol includes a recommendation that roxadustat be taken separately from phosphate binders.

As it is anticipated that other multivalent cation-containing drugs and mineral supplements (e.g., iron, calcium, magnesium, aluminum), sucralfate or magnesium- or aluminum-containing antacids would produce a similar interaction, the study protocol includes the advice that roxadustat be taken separately from these drugs.

Epoetin alfa and darbepoetin alfa have been chosen as comparators to adequately assess the efficacy, safety and benefit of achieving Hb response and maintenance in anemic subjects treated with roxadustat. These are commonly used ESAs in Europe for the treatment of anemia of ESRD, and have demonstrated their ability to correct and maintain Hb levels in this target population in several randomized controlled studies. The rules for dose adjustment and for events of excessive hematopoiesis in the present study will follow their approved posology. In case of insufficient response to epoetin alfa and/or darbepoetin alfa, rules for RBC transfusions are in place in order to assure safety of the affected study subjects.

The safety of treatment with ESA comparators in this study will be carefully monitored to include AEs, SAEs and laboratory parameters. Emphasis will be placed on cardiovascular and cerebrovascular events, which are not uncommon in the study population; an independent expert panel will assess and adjudicate all significant occurrences of such events. In addition, an independent Data Safety Monitoring Board (DSMB) will perform regular, periodic assessments of blinded and unblinded data to detect any potential safety signals that may arise during the study and advise the sponsor accordingly.

Based on the clinical and nonclinical study results to date, it is anticipated that orally administered roxadustat will be comparable in efficacy to marketed parenteral ESA products in the treatment of anemia of CKD, with an acceptable safety profile. Roxadustat may offer a valuable alternative to the current treatment options in the management of anemia of CKD.

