##### 2. *ESA* (only for subjects treated with roxadustat)

One course of rescue ESA is allowed. If the investigator considers administration of ESA as a medical necessity, 1 course of rescue ESA may be initiated if the following criteria are met:

- the Hb level has not responded adequately despite 2 or more roxadustat dose increases in the previous 8 weeks, or the roxadustat dose has reached the maximum dose limit, and
- the subject's Hb level is < 9.0 g/dL (HemoCue®) as confirmed at 2 consecutive study visits, and
- reducing the risk of alloimmunization in transplant eligible subjects and/or reduction of other RBC transfusion-related risks is a goal.

Prior to the initiation of rescue ESA (epoetin alfa for subjects treated with any epoetin prior to randomization; and darbepoetin alfa for subjects treated with darbepoetin alfa prior to randomization), the subject's Hb response, as well as factors influencing the Hb response, such as iron status, inflammatory status, hemolysis, blood loss or other potential reasons for Hb decrease should be considered and, where applicable, addressed by the investigator. Prior to initiating ESA rescue therapy, iron deficiency should be corrected (i.e. 100 ng/mL [220 pmol/L] ferritin and 20% TSAT).

The subject may continue on study, however, the subject is not allowed to be administered both rescue ESA and roxadustat during the same time period. The course of rescue ESA (i.e. the amount that may be administered) will be limited by duration of therapy and effect on Hb, including that 1 course of treatment with rescue ESA will not exceed 4 weeks in duration, and that ESA rescue will be stopped as soon as Hb  $\geq$ 9.0 g/dL as measured by HemoCue. Treatment with roxadustat may be resumed as soon as possible after the following intervals:

- At least 2 days after stop of epoetin alfa
- At least 1 week after stop of darbepoetin alfa

If a subject requires a second course of rescue with ESA, the subject must be discontinued from study treatment. The subject will complete the EOT visits (EOT visit and EOT + 2 weeks visit) and EOS visit, and will continue to be followed up at a 6-monthly frequency for vital status, SAEs and cardiovascular and thromboembolic AEs until their projected date of completion or until consent withdrawn.

**Doses:** The doses of rescue therapies are at investigator's discretion.

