In case that several Hb values are on the same day the average of these values will be used to represent the Hb of that day in the above formula. This calculation will provide the day that the change in Hb value occurs. The number of days that the Hb value has been in each category will be determined and the percentage calculated based on the length of time between the first and last Hb assessment during the evaluated period, i.e.:

Date of Last Hb assessment during the evaluated period – Date of first assessment during the evaluated period.

No imputation will be performed if no Hb value is available in relevant time windows.

In case a subject requires rescue therapy within 6 weeks prior to and during these 8-week evaluation periods, refer to Section 7.11.1 for imputation rules.

Potential Excessive Hematopoiesis (EH), regardless use of rescue therapy, based on Hb central laboratory

The presence of potential EH will be defined as:

- Hb increase by >2.0 g/dL between any 2 visits within 4 weeks of treatment

Time to first occurrence of potential EH regardless the use of rescue therapy during the treatment period will be defined in weeks as:

$$(\text{First event date} - \text{Analysis date of first dose} + 1) / 7$$

where ‘First event date’ is defined as first date of occurrence of the criterion met during the treatment period.

For a subject without potential EH, the time to censoring will be calculated (in weeks) as:

$(\text{Min}(\text{Date of last hemoglobin assessment during the Efficacy Emergent Period, End Date of the Efficacy Emergent Period}) - \text{Analysis date of first dose} + 1) / 7$

Refer to Section [7.11.6](#) for the definition of the Efficacy Emergent Period.

6.1.3.6 Occurrence (number) of hospitalizations, number of days of hospitalization per year and time to first hospitalization.

The occurrence and the number of non-HD hospitalizations per subject during the Efficacy Emergent Period will be calculated. HD days are not counted as hospitalizations, even when performed overnight.

The number of days of hospitalization per year treated will be calculated as:

$[\text{Sum of the durations of all non-HD hospitalizations in days (Date of discharge} - \text{Date of admission} + 1)] / (\text{duration of efficacy emergent period in days} / 365.25)$.

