7.4.3.5 Categorical analysis for Hb values

For the analyses below, results will be displayed by treatment arm and type of ESA treatment.

Proportion of Hb values:

The proportion of Hb values >=10 g/dL and within 10-12 g/dL is a quantitative variable in the 0 – 100 range for each subject. Descriptive statistics for this variable will be presented. This variable will be presented in weeks 28-36, in weeks 44-52 and in weeks 96 -104, on the FAS.

Percentage of time during the Efficacy Emergent Period:

Descriptive statistics for the percentage of time with Hb values falling in each interval (<10.0 g/dL, >=10 g/dL, within 10.0-12.0 g/dL, > 12.0 g/dL, > 13.0 g/dL and > 14.0 g/dL) between the first and last Hb assessment during the Efficacy Emergent Period will be presented.

The number and percentage of subjects, and the number of events, will be reported by for the following potential EH events of interest, based on Hb values from the central laboratory:

- Hb increase by >2.0 g/dL between any two visits within 4 weeks of treatment

Time to first occurrence of potential EH will also be analyzed similarly as in Section [7.4.2.7](#) (except that all data during the Efficacy Emergent Period will be taken into account for the analysis).

Subjects with at least one Hb value > 13 g/dL during the treatment period will be summarized.

7.4.3.6 Occurrence (number) of hospitalizations, number of days of hospitalization per year and time to first hospitalization during the study.

The number and percentage of subjects with hospitalization will be reported. Descriptive statistics and frequency tabulations by treatment arm and type of ESA treatment of the total duration of hospitalization (days), the average duration of each hospitalization (days), the number of hospitalizations, number of days of hospitalization per year and reason for hospitalization will also be reported.

Time to first hospitalization will also be analyzed similarly as in Section [7.4.2.7](#) (except that all data during the Efficacy Emergent Period will be taken into account for the analysis).

Superiority will be declared if the upper bound of the two-sided 95% confidence interval of the hazard ratio of the two treatment arms is below 1.

The analysis will be done on the FAS.

7.4.3.7 Occurrence and time to first use of rescue therapy, occurrence and time to first use of RBC transfusions, number of RBC packs per subject, volume of RBC transfused per subject.

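### Potential excessive hematopoiesis is analysed only regardless of rescue, so the arm comparison cannot separate rises after transfusion or rescue ESA from rises on study treatment (minor)

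*Protocol*

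**What the plan says.** **Protocol, dosing rule.** Under 5.1.2.1 (Table 4), when Hb climbs by more than 2.0 g/dL within 4 weeks in a roxadustat subject, "the dose should be reduced by 1 dose step". The note below the table makes an exception: "If a blood transfusion has been performed or a course of ESA rescue therapy has been administered within 2 weeks of meeting the criteria" for EH, "it is recommended not to perform a dose reduction for excessive hematopoiesis". In this section "All dose adjustments are made based on Hb values using HemoCue", the point-of-care device. For the ESA comparators, protocol 1.4 says: "The rules for dose adjustment and for events of excessive hematopoiesis in the present study will follow their approved posology".

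**Protocol, rescue.** Under 5.1.5, RBC transfusion is open to both arms. Rescue ESA is "only for subjects treated with roxadustat".

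**SAP, definition.** Section 6.1.3.5 heads the event "Potential Excessive Hematopoiesis (EH), regardless use of rescue therapy, based on Hb central laboratory". The criterion is a rise above 2.0 g/dL between any two visits within 4 weeks. The disregard of rescue is stated again for the time to first event.

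**SAP, analysis.** Section 7.4.3.5 reports the number of subjects and of events by arm. It adds: "Time to first occurrence of potential EH will also be analyzed similarly as in Section" 7.4.2.7, which is the Cox comparison of roxadustat with ESA.

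**SAP, handling of rescue.** The rule in 7.11.1 that sets Hb to missing for 6 weeks applies only to analyses defined without rescue, so it does not reach EH.

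**The concern.** A rise of more than 2.0 g/dL can arise in two ways. The subject may over-respond to study treatment, or may have been treated for low Hb with a transfusion or rescue ESA. The planned analysis gives both the same weight. The protocol's dosing note shows that its authors saw the difference, because it advises against acting on the rise when rescue was recent.

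The mix need not be the same in both arms. Rescue ESA exists only for roxadustat subjects, and protocol 5.1.5 does not allow it alongside roxadustat. A rise during rescue with epoetin alfa or darbepoetin alfa is therefore tabulated as EH in the roxadustat arm although roxadustat is not being given.

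Protocol 7.5 names excessive Hb response as a point of special emphasis in the safety analysis, so readers will look at this hazard ratio. Elsewhere the SAP gives both versions of an Hb endpoint. The EU primary endpoint excludes rescue and has regardless-of-rescue sensitivity analyses S3 and S4 (Table 13). Hb response has both versions (Table 18), and averaged Hb has both (6.1.3.3 and 6.1.3.4). EH has only one.

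**Working it through.** The plan states no figure to reproduce: neither document gives an expected EH rate or an expected rescue rate. The check is a comparison of the texts, followed by an illustration on assumed inputs.

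**Step 1. The texts side by side.**

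| | Protocol Table 4 and note | SAP 6.1.3.5 and 7.4.3.5 |
|---|---|---|
| Purpose | Dose decision | Arm comparison |
| Subjects | Roxadustat only | Both arms |
| Hb source | HemoCue | Central laboratory |
| Rise | >2.0 g/dL within 4 weeks | >2.0 g/dL within 4 weeks |
| Recent rescue | Criteria met, dose reduction advised against | Counted, no distinction |

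The note refers to rescue within 2 weeks of the criteria being met. It waives an action and leaves the classification as it is.

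**Step 2. Possible effect on the hazard ratio.** All inputs are assumptions:

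- e, the proportion with EH on study treatment alone, equal in both arms: 0.10 to 0.30
- r, the proportion rescued in an arm: 0.05 to 0.15
- q, the chance that rescue alone produces a qualifying rise: 0.1 to 0.5

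Observed proportion: p = e + (1 − e) × r × q. Apparent HR = ln(1 − p_rox) / ln(1 − p_ESA). The true HR is 1.00 by construction.

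Worked case with e = 0.10, q = 0.5, and rescue of 15% on roxadustat against 5% on ESA:

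- p_rox = 0.10 + 0.90 × 0.15 × 0.5 = 0.1675
- p_ESA = 0.10 + 0.90 × 0.05 × 0.5 = 0.1225
- HR = ln(0.8325) / ln(0.8775) = 1.403

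With the rescue rates swapped, the HR is 0.713. Results for rescue of 15% against 5%:

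| e | q | HR, more rescue on roxadustat | HR, more rescue on ESA |
|---|---|---|---|
| 0.10 | 0.1 | 1.092 | 0.916 |
| 0.10 | 0.5 | 1.403 | 0.713 |
| 0.20 | 0.5 | 1.212 | 0.825 |
| 0.30 | 0.5 | 1.138 | 0.879 |

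Rescue of 15% against 10% gives at most 1.170 or, reversed, 0.855. With 10% rescue in each arm and the same q, the HR is exactly 1.00. Even then, 2% to 31% of subjects with EH owe it to rescue.

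**Step 3. Equal rescue with a true difference.** Suppose true EH is 16% against 8%. The true HR is ln(0.84)/ln(0.92) = 2.09. Add 10% rescue in each arm with q = 0.4, so r × q = 0.04. The apparent HR is [ln(0.84) + ln(0.96)] / [ln(0.92) + ln(0.96)] = 1.73, so a real difference is diluted.

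**Step 4. The 4-week limit after week 36.** From week 40 visits are 4-weekly with a ±3-day window. If 4 weeks is read as 28 calendar days, and visit days are assumed uniform on −3 to +3, the chance that two consecutive on-schedule visits lie more than 28 days apart is 21/49 = 0.43. A rise between such a pair could not qualify.

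**The case against.** A reader might infer that the SAP contradicts the protocol, because the protocol exempts these rises from being EH. The text does not support that. The note assumes the criteria are met and recommends against one dosing step, for roxadustat subjects only. The protocol lists no EH endpoint, and a dosing rule and an analysis definition may differ.

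A reader might also infer that the comparison is biased against roxadustat because only that arm has rescue ESA. The documents do not support a direction. Roxadustat subjects have an alternative to transfusion, so transfusions could be more frequent in the ESA arm. Rescue ESA requires Hb below 9.0 g/dL at two consecutive visits, lasts at most 4 weeks and stops once Hb reaches 9.0 g/dL. A subject starting at 8.5 would have to pass 10.5 to qualify, so q for rescue ESA may be low.

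The SAP's choice is also explicit, and the event is labelled potential. Overshoot by level is covered elsewhere: time above 12, 13 and 14 g/dL, and subjects with any value above 13. Rescue use is tabulated by arm.

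The strongest argument is against replacing the main definition. In the ESA arm, a rise after an ESA dose increase is a rise on study treatment and always counts. Leaving out rises after rescue ESA drops ESA-driven rises from the roxadustat arm only.

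All of this stands. It rules out a claim of contradiction, of known bias, or of a wrong main definition. It leaves one gap: neither the level summaries nor the separate rescue tables show which EH events followed rescue.

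**Conclusion.** The point holds as a gap in the supporting analyses. Potential EH is defined and compared only regardless of rescue, so its hazard ratio mixes response to study treatment with the effect of treating low Hb, and nothing planned separates them.

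The size and direction are unknown. With no true difference, equal rescue and equal response to it, the effect on the hazard ratio is nil. Over the assumed ranges of unequal rescue, the apparent HR runs from about 0.7 to 1.4. Those limits come from invented rates and are not a prediction.

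Severity is minor. EH is an additional analysis outside the primary and key secondary tests. It is not itemised in SAP Table 6, and 7.4.3.5 states no success criterion for it. The 4-week point is smaller still: it depends on a calendar-day reading and on assumed visit timing, it affects both arms, and unscheduled central-laboratory samples can fill some gaps.

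**What to change.** Keep the stated analysis. In SAP 6.1.3.5 and 7.4.3.5 add a supplementary potential-EH analysis in both arms (subjects, events and time to first event). It should not count a rise whose later Hb falls within 2 weeks after an RBC transfusion or rescue ESA, the window in the protocol's note. For a rescue course of more than one day, state that the window runs from its first administration to 2 weeks after its last. State also that the SAP event differs from the protocol's dosing criterion in Hb source and in its treatment of rescue.

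As a minor clarification, say that after week 36 consecutive scheduled analysis visits count as within 4 weeks even if they fall more than 28 days apart inside the visit window.

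The cost is a few sentences and one derived flag, since rescue details are already recorded in the eCRF. The supplementary analysis will have slightly fewer events. It removes ESA-driven rises from the roxadustat arm only, and this should be noted where it is reported. A 2-week window will also leave in some later rises measured from a pre-rescue value. A wider window would remove more of these but could hide genuine overshoot after roxadustat resumes.

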## **Subjects receiving ESA (epoetin alfa or darbepoetin alfa)**

All dose adjustments are made based on Hb values using HemoCue®, a point-of-care device. Dose adjustments will aim at keeping subjects' Hb level between 10.0 to 12.0 g/dL.

During the treatment period, the active comparator drugs epoetin alfa (Eprex®) and darbepoetin alfa (Aranesp®) will be provided by the sponsor. Dosing, dosing frequencies and dose adjustments should be in accordance with the UK SmPC for Eprex® and EU SmPC for Aranesp®. The protocol-specified frequencies are once weekly, twice weekly or TIW for epoetin alfa; and once weekly or once every other week for darbepoetin alfa. In addition, the protocol allows for administration of epoetin alfa once every other week and darbepoetin alfa once every 4 weeks. These frequencies are only to be used in subjects on low ESA doses that do not fit into the normal frequencies of administration and if deemed clinically appropriate. Contact the medical monitor if dose adjustments would lead to doses lower than 1000 IU epoetin once every other week or 10 µg darbepoetin once every 4 weeks. For PD subjects, darbepoetin dosing every 4 weeks is allowed.

### **5.1.3 Previous and Concomitant Treatment**

#### **5.1.3.1 Previous Medication**

Previous medications are any prescription or over-the-counter preparations, including herbal products and “natural remedies”, used by a subject prior to screening.

If not specified differently, intake of any medication within 4 months prior to randomization should be documented in the eCRF. The medication name, start and stop date, route, dose and frequency, and indication for each medication will be entered in the eCRF.

The last treatment course of any prior treatment received for anemia (medication or procedures such as ESAs, oral or IV iron, and RBC transfusions) within 12 months prior to randomization will be documented in the eCRF.

Certain prior medications are prohibited for a specified time frame prior and/or during the study treatment period and/or until EOS. These medications and restrictions are described in Section [5.1.3.3](#)

